9.7. Power Analysis

9.7.1. Primary Analyses

Based on previously published IPF clinical trials, the PL group is expected to experience a drop in FVC of approximately 0.20 L over the study period (see Figure 1). The IPFnet Steering Group determined a clinically important difference would be to preserve the majority of the decline relative to PL over the study period. In particular, a treatment effect of 0.15 L was determined to be a clinically meaningful difference. Potential dropout is a key factor in the proposed study. The drop-out process assumed 5% lost to follow-up after every study visit. Only 80% of subjects were assumed to be followed for the entire study period. All models assumed a compound symmetry structure for the covariance matrix. Power calculations were performed using a SAS IML program for designing repeated measures studies.⁴⁶ Based on preliminary reviews of the data from the University of Michigan, the covariance matrix parameters were estimated at approximately $\sigma^2 = 0.757$ (variance parameter) and $\rho = 0.936$ (correlation parameter). To be conservative, the power calculations for the primary analysis were performed with parameter setting of $\sigma^2 = 0.810$ (variance parameter) and $\rho = 0.925$ (correlation parameter).

The power calculations assume a correction for imperfect compliance proposed by Lachin and Foulkes to allow for 2% noncompliance for each of the treatment arms.⁴⁷ Thus, the sample size of 130 subjects per arm would be reduced to an adjusted sample size of $130 \times (1 - 0.02 - 0.02)^2 = 119.8$ or 120 subjects per arm.

Under the assumed Type I error rate of 0.05, with a correlation parameter of 0.925 and standard deviation of 0.90, the difference of 0.15 L (or 0.0025 L/week) shown in Table 6 would have power of 93%.

Table 6: Hypothetical Values of Mean FVC (L) Change from Baseline

	Week 15	Week 30	Week 45	Week 60
NAC	0.0125	0.0250	0.0375	0.0500
Placebo	0.0500	0.1000	0.1500	0.2000
Difference	0.0375	0.0750	0.1125	0.1500

Abbreviations: FVC, forced vital capacity; PL, placebo

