IPFnet

PANTHER-IPF
**PREDNISON, AZATHIOPRINE,
AND N-ACETYLCYSTEINE:
A STUDY THAT EVALUATES RESPONSE IN
IDIOPATHIC PULMONARY FIBROSIS
*A RANDOMIZED, DOUBLE-BLIND, PLACEBO-CONTROLLED TRIAL***

Compiled by:

The PANTHER-IPF Protocol Committee

Version Date: May 19, 2009

Amendment 1 Date: May 28, 2010

Amendment 2 Date: December 6, 2011

Distributed by:

The IPFnet Coordinating Center
Duke Clinical Research Institute
Duke University
[name]
[name]

Protocol Summary

PRODUCT	N-acetylcysteine
CLINICALTRIALS.GOV NUMBER	NCT00650091
PROTOCOL TITLE	Prednisone, Azathioprine, and N-acetylcysteine: A Study THat Evaluates Response in Idiopathic Pulmonary Fibrosis (PANTHER-IPF)
DIAGNOSIS AND MAIN CRITERIA FOR INCLUSION	Confirmed idiopathic pulmonary fibrosis, diagnosed within 48 months of enrollment; forced vital capacity \geq 50% predicted; hemoglobin adjusted diffusing capacity of the lung \geq 30% predicted
STUDY OBJECTIVES	To assess the safety and efficacy of N-acetylcysteine in subjects with newly diagnosed idiopathic pulmonary fibrosis
STUDY DESIGN	Multi-center, randomized, double-blind, placebo-controlled
TREATMENT REGIMENS	1) N-acetylcysteine (600 mg TID), or 2) placebo
ROUTE OF ADMINISTRATION	Oral
TIME BETWEEN FIRST AND LAST DOSES OF ACTIVE STUDY AGENT	Maximum of 60 weeks
NUMBER OF SUBJECTS	Approximately 130 NAC, 130 placebo (1:1)
NUMBER OF CLINICAL CENTERS	Approximately 26 US sites
PRIMARY ENDPOINT	Change in longitudinal forced vital capacity measurements over 60 weeks
INTERIM ANALYSIS	Completed October 2011

Study Sponsor: National Heart Lung and Blood Institute

Acting Steering Group Chair: **[name]**
University of Colorado - Denver

Project Officer: **[name]**
National Heart Lung and Blood Institute
Bethesda, MD

Protocol Committee Cochairs:

[name]
University of Washington

[name]
University of Michigan

Data Coordinating Center:

Duke Clinical Research Institute
Duke University

Table of Contents

List of Tables 7

List of Figures 7

List of Abbreviations 8

1. Summary 12

2. Hypotheses and Specific Aims 13

 2.1. Null Hypothesis..... 13

 2.2. Specific Aim 1 13

 2.3. Specific Aim 2 13

 2.4. Prespecified Subgroups of Interest..... 14

3. Background and Significance 15

 3.1. Idiopathic Pulmonary Fibrosis is the Most Common Interstitial Lung Disease..... 15

 3.2. Rationale for Placebo Control 15

 3.3. Rationale for N-acetylcysteine..... 16

 3.5. Rationale for N-acetylcysteine as a Stand-alone Therapy..... 17

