2.1. Null Hypothesis

Treatment with NAC will provide the same efficacy as PL, as measured by longitudinal changes in FVC.

2.2. Specific Aim 1

This study is designed to assess the safety and efficacy of NAC in subjects with newly diagnosed IPF.

2.3. Specific Aim 2

Secondary goals of this study are to assess differences between treatment groups for the following:

1. Mortality
2. Time to death
3. Frequency of acute exacerbations (AExs)
4. Frequency of maintained FVC response
5. Time-to-disease progression
6. Change in DLCO
7. Change in Composite Physiologic Index (CPI)
8. Change in resting alveolar-arterial oxygen gradient
9. Change in 6-minute walk test (6MWT) distance
10. Change in 6MWT oxygen saturation area under the curve
11. Change in 6MWT distance to desaturation < 80%
12. Change in 6MWT minutes walked
13. Changes in health status as measured by the SF-36, EuroQol, and St. George's Respiratory Questionnaire (SGRQ)
14. Changes in dyspnea as measured by the University of California at San Diego Shortness of Breath Questionnaire (UCSD SOBQ)
15. Frequency and types of adverse events (AEs)
16. Frequency and types of respiratory complications, both infectious and noninfectious
17. Frequency of hospitalizations, both all-cause and respiratory-related

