9.1. General Analytic Considerations

All primary analyses will be based on intent-to-treat (ITT) principles using all randomized subjects. Baseline factors across groups will be compared using mean (standard deviation) and median (25th and 75th percentiles) summary measures. Kaplan-Meier curves will be used to display event rates. Due to clinical interest in departures from both sides of the null hypothesis, all test statistics will be 2-sided.

Reasonable caution needs to be taken when conducting multiple analyses on key clinical subgroups. For subgroup analyses, a conservative significance level of 0.001 will be used for all interaction tests. Thus, subgroup comparisons will be considered exploratory unless the p-value from the interaction test is smaller than 0.001.

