10.4. Recommendations on Interim Monitoring of Efficacy, Safety, and Futility

First and foremost the role of the DSMB will be to review subject safety and trial conduct at periodic points during the study. The DSMB may require analyses of the primary endpoint results for comparing the benefit and risks of treatment strategies. The benefit of collecting additional data on key secondary endpoints, with extended follow-up, and establishing a robust

evidence base for determining a standard of care will need to be carefully considered before early termination of one or more treatment arms. After careful consideration, the IPFnet Steering Group recommends conservative thresholds for the early examinations of the safety and efficacy data.

The DSMB will be expected to meet approximately every 6 months until trial completion to review safety and toxicity data. The DSMB may recommend stopping the study based on these reviews. Because the DSMB could stop the trial for safety concerns as well as for a large efficacy benefit, there could be multiple opportunities to reject the null hypothesis (no difference in event rates between the PL and NAC groups). A Bonferroni approximation will be applied during the one planned interim analysis for efficacy.

Before locking the database, a statistical analysis plan (SAP) will be developed to provide complete details on the statistical analysis. The SAP will include the specifics for how and when the DSMB will be notified for AEs. The IPFnet DCC will deliver to the DSMB all FDA-defined AEs at 3-month intervals. The IPFnet DCC will prepare narrative SAE reports in real time for DSMB review including recommendations and analysis of similar events for each SAE submitted to the FDA.

11. Investigator and Sponsor Obligations

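### The 93% power in Protocol section 9.7.1 uses the full 0.05 and deducts nothing for the Bonferroni-corrected efficacy interim in section 10.4

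*Protocol*

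**What the plan says.** Section 9.7.1 sets out the power calculation "Under the assumed Type I error rate of 0.05, with a correlation parameter of 0.925 and standard deviation of 0.90", and says that "the difference of 0.15 L (or 0.0025 L/week) shown in Table 6" has 93% power with 120 subjects per arm after the noncompliance correction. It does not mention an interim look. Section 9.1 makes the test two-sided: "Due to clinical interest in departures from both sides of the null hypothesis, all test statistics will be 2-sided".

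Section 10.4 warns that "there could be multiple opportunities to reject the null hypothesis (no difference in event rates between the PL and NAC groups"), and continues: "A Bonferroni approximation will be applied during the one planned interim analysis for efficacy". It gives no number for the interim or the final level, only a general preference for cautious limits at early looks.

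The Protocol Summary gives the interim analysis as "Completed October 2011". Section 1 counts the subjects already enrolled at that point towards the final 130 per arm.

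The trial's null in section 2.1 is "Treatment with NAC will provide the same efficacy as PL, as measured by longitudinal changes in FVC". Section 5.1 makes change in FVC the primary endpoint, and section 9.4 tests it as a difference in slopes.

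**The concern.** Sections 9.7.1 and 10.4 describe the same NAC–placebo comparison but do not share one alpha budget. A Bonferroni correction over an interim and a final look divides the 0.05 between them. What the interim receives is not available at the end. The power statement uses all of it.

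Two things are at stake. If the final test follows the correction, its power is below the stated 93%. If it ignores the correction and uses 0.05, the error rate over both looks can exceed 5%. Under an equal split, a final p-value between 0.025 and 0.05 would have a disputed status.

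Section 10.4 also words the monitored null in terms of event rates, which is not the trial's primary hypothesis. This makes it harder to see which alpha the correction protects.

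**Working it through.** **Inputs** (sections 9.1, 9.4 and 9.7.1): visits at weeks 0, 15, 30, 45 and 60; compound symmetry with variance 0.81 and correlation 0.925; 5% loss after each visit, with 80% followed to the end; 120 per arm; slope difference 0.0025 L/week; two-sided test.

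**Formula.** A subject seen at the first m visits has design matrix X = [1, t] and covariance V = 0.81 × [(1 − 0.925) I + 0.925 J], where J is the matrix of ones. Average XᵀV⁻¹X over the dropout patterns: 5% of subjects stop after each of visits 1 to 4, and 80% complete. The average information per subject has entries 1.3069 (intercept), 34.448 (cross term) and 32,015.5 (slope).

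- Slope variance per arm = 1.3069 / (1.3069 × 32,015.5 − 34.448²) / 120 = 2.679 × 10⁻⁷
- SE of the slope difference = √(2 × 2.679 × 10⁻⁷) = 0.000732 L/week, or 0.0439 L over 60 weeks
- Power = Φ(0.0025/SE − z) = Φ(3.415 − z), with z the two-sided critical value

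**Reproducing the stated figure.** At 0.05, Φ(3.415 − 1.960) = 92.7%. If the 5% loss is instead compounded (0.95 per visit), SE = 0.000728 and power is 93.0%. Both agree with 93%. A one-sided 0.05 would give about 96% and does not. The published figure therefore uses the full two-sided 0.05.

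**Power after a Bonferroni split.** The splits are assumptions, because the protocol gives none. The range covers the two dropout versions.

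| Interim alpha | Final alpha | Critical z | Power |
|---|---|---|---|
| none deducted | 0.05 | 1.960 | 92.7–93.0% |
| 0.001 | 0.049 | 1.969 | 92.6–92.9% |
| 0.005 | 0.045 | 2.005 | 92.1–92.4% |
| 0.01 | 0.04 | 2.054 | 91.3–91.6% |
| 0.025 | 0.025 | 2.241 | 88.0–88.4% |

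**Overall type I error if the final test still uses 0.05.** Treat the two test statistics as bivariate normal with correlation √f, where f is the information fraction at the interim. The protocol does not give f, so I used 0.3 to 0.7.

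- Interim at 0.025: 6.8% at f = 0.3, 6.4% at f = 0.5, 5.9% at f = 0.7 (Bonferroni bound 0.025 + 0.05 = 7.5%)
- Interim at 0.001: 5.0–5.1% throughout (bound 5.1%)

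**The case against.** A reader might infer that the protocol tests the final comparison at 0.05, and that 5% error and 93% power therefore cannot both hold. The text does not support this. The 0.05 appears only as the assumed rate in the power calculation, and section 9.4 names no level for the final test. With 0.001 at the interim and 0.049 at the end, overall error is at most 5% and power is 92.6–92.9%, which still rounds to 93%. The cautious attitude to early looks in section 10.4 is compatible with such a split. Section 10.4 also leaves full analysis details to an SAP, which may fix the split, so its absence here is not in itself the fault.

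A reader might also infer from the event-rate wording that the correction belongs to a different hypothesis. Sections 2.1 and 5.1 fix FVC as the null and the primary endpoint, and section 10.4 itself provides for analyses of the primary endpoint. The wording is a slip.

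Two further objections carry some weight. The protocol reports the October 2011 outcome only for the triple-therapy arm. It does not say what alpha, if any, the NAC–placebo comparison used, and the correction is still written in the future tense. Also, section 9.7.1 chose cautious variance parameters. With its own estimates (0.757 and 0.936), power at 0.025 would be 94.3–94.6%, so the trial is not shown to be underpowered.

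These objections limit the size of the point but do not remove it. The protocol itself states both the 0.05 behind the 93% and the Bonferroni rule, and the first makes no allowance for the second.

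**Conclusion.** The point holds as a moderate one. The 93% is the power at the full two-sided 0.05, while the protocol's own monitoring rule assigns part of that alpha to a completed look at the same comparison, in subjects who stay in the final analysis. The overstatement runs from negligible (interim at 0.001) through one to two points (0.005–0.01) to about five points (equal split, 88%). An inflated error rate of 5.9–6.8% arises only if the interim used 0.025 and the final test nevertheless uses 0.05, for information fractions 0.7 to 0.3. All of these sizes rest on assumed splits. If no alpha was used for NAC versus placebo in October 2011, there is nothing to deduct, and the protocol should say so.

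**What to change.** In section 9.7.1, replace the 0.05 and 93% with the two-sided alpha that remains for the final NAC–placebo test after the interim and the power at that alpha (88% if it is 0.025), and test the final comparison at that alpha. In section 10.4, replace event rates with the FVC slope difference.

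The cost is a few sentences and a slightly less favourable power figure. No new patients are needed. Holding 93% at a final alpha of 0.025 would take about 142 adjusted subjects per arm, or 142.1/0.96² ≈ 154 randomized, but restating the power is enough.

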9.7.2. Power Analysis for Secondary Endpoints

Power calculations for secondary endpoint measurements are shown in Table 7. Standard deviations are based on unpublished data provided by the University of Michigan. The calculations are based on a 2-sample t-test with Type I error rate set at 0.05. These calculations are likely to be conservative because the statistical approach, described in section 9.5, for analyzing these endpoints will incorporate incomplete observations as well as intermediate data points.

Table 7: Detectable Differences in Treatment Means for Selected Endpoint Measurements

Secondary Endpoints	Std Dev of the Baseline Score	Detectable Difference for 80% Power	Std Dev of the Change Score	Difference Detectable for 80% Power
DLCO%pred	16.6	5.8	9.1	3.2
6MWT Area Under the Desaturation Curve	21.9	7.6	17.5	6.1
6MWT Distance to Desaturation	22.4	7.8	31.5	11.0
6MWT Minutes Walked	2.10	0.73	2.05	0.71

Abbreviations: Std Dev, standard deviation; DLCO%pred, diffusing capacity of the lung for carbon monoxide percent predicted; 6MWT, 6-minute walk test

10. Study Administration

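### Table 7's detectable differences rest on 130 complete, compliant subjects per arm; on section 9.7.1's own attrition the change-score power falls below the stated 80%, so calling the figures conservative is not supported

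*Protocol*

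**What the plan says.** Section 9.7.2 describes the method for the secondary endpoints: "The calculations are based on a 2-sample t-test with Type I error rate set at 0.05". Section 9.1 makes the tests two-sided: "all test statistics will be 2-sided". Table 7 lists four endpoints. For each it gives a baseline-score standard deviation and a change-score standard deviation, with the "Detectable Difference for 80% Power" beside each. The first row reads "DLCO%pred 16.6 5.8 9.1 3.2". No sample size, dropout rate or compliance correction is stated. The text then says "These calculations are likely to be conservative because the statistical approach" of section 9.5 will make use of incomplete observations and intermediate data points.

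Section 9.7.1, on the primary endpoint, works on a different basis. It takes 5% loss after every visit and says "Only 80% of subjects were assumed to be followed for the entire study period". For noncompliance, "the sample size of 130 subjects per arm would be reduced to an adjusted sample size of" 120. The Protocol Summary gives the planned enrollment as "Approximately 130 NAC, 130 placebo (1:1").

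**The concern.** Two adjoining power calculations for the same trial appear to use different numbers of subjects. The primary calculation is discounted for loss and noncompliance; the secondary one apparently is not, yet it is the one described as conservative.

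The reason given does not fit that starting point. Partial records recover some of the information that dropout removes. A calculation that removed nothing has nothing to recover, so this argument would work only against a completer-based sample size.

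Table 7 tells a reader how sensitive the trial is for DLCO and three 6MWT measures, and changes in DLCO and in 6MWT measures are listed among the secondary goals in section 2.3. If the stated sensitivity is too favourable, a null secondary result may be taken to exclude more than it does.

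**Working it through.** **Inputs.** Two-sided alpha 0.05 and 80% power (sections 9.1 and 9.7.2). Standard deviations (SDs) and differences from Table 7. 130 per arm (Protocol Summary). Loss of 5% after each visit, 80% complete, noncompliance factor (1 - 0.02 - 0.02)^2 = 0.9216 (section 9.7.1). Measurement times: 6MWT at baseline, week 30 and week 60 (section 9.5); DLCO at screening, week 30 and week 60 (sections 4.4.2.1, 4.4.2.4 and 4.4.2.6, and Table 3).

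**Step 1: reproduce Table 7.** Detectable difference = (1.96 + 0.84) x SD x sqrt(2/n), or the exact t version. The exact t results, baseline-score column / change-score column, are:

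| Endpoint | Printed | n = 130 | n = 120 |
|---|---|---|---|
| DLCO%pred | 5.8 / 3.2 | 5.79 / 3.17 | 6.03 / 3.31 |
| Desaturation area | 7.6 / 6.1 | 7.64 / 6.10 | 7.95 / 6.36 |
| Distance to desaturation | 7.8 / 11.0 | 7.81 / 10.99 | 8.14 / 11.44 |
| Minutes walked | 0.73 / 0.71 | 0.732 / 0.715 | 0.763 / 0.744 |

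Of the sizes tried (130, 120, 104, 96), only 130 fits. For minutes the change-score entry matches through the normal approximation, 0.712. The table therefore carries neither attrition nor noncompliance.

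**Step 2: completer t-test on section 9.7.1's assumptions.** With attrition only, n = 130 x 0.80 = 104, and power at the printed differences is 70-72%. With both corrections, n = 130 x 0.80 x 0.9216 = 95.8, about 96, and power is 67-68%. The change-score differences for 80% power become 3.7, 7.1, 12.8 and 0.83.

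**Step 3: repeated-measures model.** Sections 9.4 and 9.5 treat the enrollment value as a response, with treatment, time and time by treatment. With visits at weeks 0, 30 and 60, the 5% loss per visit leaves 10% with baseline only, 10% through week 30 and 80% complete. Take V = SD^2 x [(1 - rho)I + rho J], where SD is the baseline-score SD and J is the matrix of ones, with rho = 1 - SDchange^2 / (2 x SDbaseline^2). For DLCO, rho = 1 - 9.1^2 / (2 x 16.6^2) = 0.85. The others are 0.68, 0.01 and 0.52. The information is the sum over dropout patterns of n x fraction x X'V^-1 X. The contrast is the treatment difference in change from week 0 to week 60.

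Power = Phi(difference / SE - 1.96), and the 80%-power difference = 2.80 x SE. For DLCO with both corrections: 3.2 / 1.290 - 1.96 = 0.52, giving 70%; 2.80 x 1.290 = 3.6.

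| Endpoint (change score) | Printed | Power, attrition only | SE, both corrections | Power, both | 80%-power difference, both |
|---|---|---|---|---|---|
| DLCO%pred | 3.2 | 73% | 1.290 | 70% | 3.6 |
| Desaturation area | 6.1 | 73% | 2.468 | 70% | 6.9 |
| Distance to desaturation | 11.0 | 76% | 4.32 | 72% | 12.1 |
| Minutes walked | 0.71 | 73% | 0.2875 | 70% | 0.81 |

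Treating time as linear rather than categorical changes these powers by no more than about 0.2 percentage points. The recomputed differences exceed the printed ones by about 10-13% (for example 12.1 / 11.0 = 1.10 and 6.9 / 6.1 = 1.13).

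**Step 4: does the intermediate visit help?** With complete data and compound symmetry, the week-30 value adds nothing to the week 0 to 60 contrast in this model. The detectable differences stay at 3.16, 6.08, 10.95 and 0.71.

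**Step 5: check of method.** The same code with a linear slope, 120 per arm, five visits, rho 0.925 and SD 0.90 gives 92.7% for the primary endpoint, against the stated 93%.

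**The case against.** The table's arithmetic is right for its stated method, the wording is hedged with likely, and Table 7 sizes nothing. These points stand, but they do not supply the missing basis. Five further objections have weight.

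- **Baseline adjustment.** If baseline means were constrained equal, or the model conditioned on baseline, power with both corrections would be about 73% for DLCO, 76-77% for area, 79-81% for minutes and over 90% for distance. With attrition alone it is 76%, 79-80%, 82-84% and 94-98%. Section 9.5 mentions unnamed baseline risk factors but does not state this adjustment, and section 9.7.2 does not rely on it. This narrows the point, because for distance the printed change-score figure could well be conservative.
- **Noncompliance.** The factor appears only under the primary analysis. Without it the shortfall is roughly halved, to 73-76%.
- **DLCO visits.** Section 9.5 speaks of pulmonary function tests every 15 weeks. On that reading, with a linear slope and both corrections, the DLCO difference is 3.2 at 80% power, exactly as printed. The visit sections and Table 3 give DLCO only one intermediate visit, so the two places conflict. With five visits and categorical time, power is still about 71%.
- **Early-withdrawal visit.** DLCO and 6MWT are scheduled there, so some who leave early would add a measurement. Subjects lost to follow-up would not.
- **Implied correlations.** They assume equal variances across visits. The 0.01 for distance is implausibly precise, and 12.1 should be read as approximate.

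A reader might infer that the whole of Table 7 has about 70% power. The documents do not support that. Under the change contrast with both corrections, the baseline-score entries have about 99% (DLCO), 87% (area), 44% (distance) and 72% (minutes), so no single figure describes the table.

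**Conclusion.** The point holds in limited form. Table 7 is computed for 130 complete, compliant subjects per arm without saying so, which is inconsistent with the follow-up and compliance assumed one subsection earlier. The reason given for conservatism does not hold against that complete-data benchmark.

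On the three-visit schedule, with the enrollment value as a response and no further baseline adjustment, the printed change-score differences have about 73-76% power with attrition alone and 70-72% with both corrections. The completer t-test with both corrections gives 67-68%. These repeated-measures figures rest on compound symmetry and on correlations derived from Table 7's own standard deviations. The sample size behind Table 7 is inferred, though firmly. Compounding the 5% loss gives 0.95^4 = 81.5% completers rather than 80%, which does not alter the conclusion.

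The shortfall is firmest for DLCO, which stays below 80% in every three-visit version examined. Desaturation area comes next: below 80% with both corrections, and at 79-80% with attrition alone if baseline means are constrained. Minutes and distance depend on whether the analysis conditions on baseline.

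A reader might also conclude that every secondary figure is optimistic, or that the trial is undersized. Neither follows: distance may be conservative under a baseline-adjusted model, and the primary 93% already includes both corrections and reproduces.

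**What to change.** In section 9.7.2, state the number per arm and the follow-up assumed for Table 7. Recompute the table under section 9.7.1's attrition, with the noncompliance factor if it is meant to apply to secondary endpoints, and for the intended model, saying whether that model conditions on baseline. Remove the blanket statement that the figures are likely to be conservative, or confine it to endpoints for which the recomputation shows it. Reconcile the DLCO measurement times between section 9.5 and Table 3, since the DLCO figure depends on them.

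If the table is not recomputed, the minimum is a note that it assumes 130 per arm with complete follow-up and full compliance, with the conservatism claim deleted.

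The cost is one table and one or two sentences, with somewhat less favourable secondary figures. Sample size, conduct and the primary analysis do not change.
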